STUDY PROTOCOL

Official Title: Parental Nutrition Education on the Performance and Body Composition of Young Basketball Players (PNE-YBP)

Unique Protocol ID: GO 2023/206

NCT Number: Not yet assigned (Pending Registration)

Date: December 22, 2025

Principal Investigator: [name]

Participant

This study involved 30 young basketball players, aged 8 to 13 years, who participated in the Burdur Mehmet Akif Ersoy University Basketball team from May to July 2023. A single-group pre-post quasi-experimental design was used. The sample size was determined based on feasibility within the basketball team context. A post-hoc power analysis was performed using G*Power 3.1 software for a two-tailed paired-sample t-test. With an α level of 0.05, a sample of 30 participants, and an observed large effect size (Cohen's $d = 0.8$), the achieved statistical power ($1 - \beta$) was 0.95. Therefore, the study was sufficiently powered to detect medium-to-large differences between pre- and post-education measurements. This power level is consistent with previous intervention studies in young or adolescent athletes (5, 17, 18).

Ethics approval

The parents of the players involved in the study were informed about the research; the informed consent form was obtained from all of parents. Prior to commencing the study, ethical approval was secured from the Burdur Mehmet Akif Ersoy University Non-Interventional Research Ethics Committee (Approval No: GO 2023/206, Date: April 5, 2023) before beginning of data collection.

Procedures

Before the start of the study, a questionnaire developed by the researchers was administered to the parents (see additional file 1). This questionnaire included socio-demographic data, eating habits, and an assessment of sports nutrition knowledge for young adolescent players. At the same time, anthropometric measurements of young adolescent players were taken prior to the beginning of sports nutrition education and performance tests. A retrospective 3-day food consumption record form was utilized employing the retrospective recall method. Food consumption was recorded over two weekdays and one weekend day, with the data presented as the average for the three days. The same questionnaire and forms were administered to the

parents post-training, and the performance and anthropometric measurements of the players were reassessed education. Training volume was assessed using a self-reported training diary completed by the players and verified by their coaches. Players recorded the duration (minutes per session) and frequency (sessions per week) of their training over the previous four weeks. Weekly training volume was calculated as the product of session duration and frequency (minutes/week). Assessments were repeated 4 weeks after baseline. The Nutrition Knowledge Level Test was utilized to assess the sports nutrition knowledge of parents and evaluate the effectiveness of the education provided on this topic.

Sport Nutrition Knowledge Level Test

The Sports Nutrition Knowledge Level Test (SNKT) was created by Torres-McGehee et al. (19) and then adapted into Turkish by Dener (20). The test consists of 20 questions, with a scoring scale of 100 points. Each question is assigned a value of 5 points for a correct answer and 0 points for an incorrect response. A correct response to 15 questions (greater than 75 points) demonstrates a sufficient level of knowledge. Higher scores indicate a greater level of sport nutrition knowledge.

Dietary Assessment

The players' parents were requested to complete the 3-day food consumption record form in detail, utilizing the retrospective recall method for the young basketball players. Players were instructed to complete a 3-day food consumption record over three consecutive days (Thursday, Friday, Saturday, or Sunday, Monday, Tuesday), ensuring that one of these days fell on the weekend. They were required to document the foods consumed, including water, along with the quantity (weight, portion), cooking method, and food content. Meal and Food Photograph Catalog (21) and Standard Recipes for Caterings (22) books were used to determine the food quantities and the amounts included in the portions of the meals. The completed food consumption record was subsequently entered into the Nutrition Information System (BEBİS

8.0, Stuttgart, Germany). All 3-day dietary records were analyzed and entered into the Nutrition Information System by the same registered dietitian to ensure consistency in data interpretation and nutrient coding. The Nutrition Information System used in this study has been previously validated for estimating macro- and micronutrient intakes in Turkish populations (23). The mean daily intake levels of energy, macronutrients, and micronutrients for the players were evaluated.

Anthropometric Measurements

Anthropometric measurements such as height, body weight, Body Mass Index (BMI), and body composition were conducted to evaluate nutritional status and monitoring growth. Height was measured with feet positioned side by side and the head in line in the Frankfort plane, ensuring the eye triangle and auricle were at the same level and parallel to the ground. Body weight was recorded with players removing their shoes and wearing light clothing. The device quantifies weight in kg with an accuracy of 0.1 kg. To ensure accurate weight measurement, it was considered that individuals had fasted for a minimum of 4 hours, refrained from fluid intake, and did not experience frequent urination. The calculation of BMI involves dividing an athlete's body weight in kilograms (kg) by the square of their height in meters (m^2). Waist circumference was assessed at the midpoint between the lowest rib and the crista iliac crest using a non-elastic tape measure. Prior to the measurement of waist circumference, individuals were instructed to remove any items and clothing that could obstruct the measurement process. To ensure accurate measurement, the individual stood upright with a relaxed abdomen, arms positioned at their sides, feet together, and faced directly towards the person conducting the measurement. The measurements were documented in centimeters with a precision of 0.1 cm. Hip circumference was assessed with the players in a lateral position, measuring from the highest point parallel to the floor using a non-stretchable plastic measuring tape. The players' body compositions were assessed on a non-training day, in a fasted state, wearing light clothing, utilizing bioelectrical

impedance analysis (BIA). Basal metabolic rate was estimated via the BIA device output. To reduce variability, all measurements were taken by the same trained operator at the same time of day (morning) under standard conditions. Participants arrived after fasting for at least four hours, avoided drinking fluids, caffeine, and vigorous exercise for at least 12 hours, emptied their bladders within 30 minutes of the assessment, took off any metal accessories, and were measured barefoot in light clothing in a room temperature (about 22-24 °C). The order of the measurements stayed the same for all sessions, and the device checks that the manufacturer suggested were done before each session.

Performance Tests

Physical performance tests were conducted to assess the players' speed, strength, and endurance. The testing session included a 20-m sprint, vertical jump, handgrip strength, and sit-and-reach flexibility test. All procedures followed validated protocols recommended by the American College of Sports Medicine (24) and the European College of Sport Science (25). Tests were performed in the following order to minimize fatigue effects: flexibility, handgrip strength, vertical jump, and 20-m sprint. Each participant was allowed one familiarization trial per test and two recorded attempts, with the best score used for analysis. Handgrip strength was measured using a Takei 5401 digital dynamometer, vertical jump performance with a Smart Jump System, and sprint time with photocell timing gates. All tests were supervised by trained researchers to ensure standardization and reliability.

Nutrition Education Module

The nutrition education presentation was carried out by the researchers in a single 90-minute session online (via Zoom) following the initial questionnaire, performance tests, and anthropometric measurements. The session involved young basketball players, their parents (e.g. mother, father and/or other primary caregivers), and team coaches to ensure a consistent nutrition message across family and sports settings. The nutrition education encompassed the

macro and micronutrients essential for adolescents during their growth and development, detailing their required quantities and significance in sports nutrition, healthy meal choices, and guidelines for consumption before, during, and after competitions and training sessions. The importance of water intake was elucidated, and guidance was offered regarding the adequate fluid consumption throughout training and competition. The session concluded with a Q&A segment of young players and their parents regarding nutritional management.

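### One group measured twice, four weeks apart, can describe change but cannot show that the education caused it; the effectiveness wording should be replaced

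*Protocol*

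**What the plan says.** The Participant section describes the sample and the design: "This study involved 30 young basketball players, aged 8 to 13 years" and "A single-group pre-post quasi-experimental design was used". The size was not derived from a target effect: "The sample size was determined based on feasibility within the basketball team context". The power statement there refers to a two-sided paired t-test at alpha 0.05.

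The Procedures section places reassessment four weeks after baseline. It gives the parents the same questionnaire and forms again, and says that the knowledge test serves to "evaluate the effectiveness of the education provided on this topic". The official title is "Parental Nutrition Education on the Performance and Body Composition of Young Basketball Players".

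Three other sections describe what else happens in the interval or at retest:

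- **Growth.** Anthropometric Measurements lists growth monitoring among the reasons for measuring.
- **Training.** The players belong to a university basketball team. Procedures has a coach-verified diary: "Players recorded the duration (minutes per session) and frequency (sessions per week) of their training over the previous four weeks".
- **Retesting.** Performance Tests says: "Each participant was allowed one familiarization trial per test and two recorded attempts, with the best score used for analysis".

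The intervention, in Nutrition Education Module, is one 90-minute online session. No control group, waiting list, repeated baseline or historical comparator is described.

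**The concern.** With one group and two time points, the only available contrast is the mean change. Any effect of the education and any other shift over the same four weeks enter that one number. A larger sample, more precise measurement or a different test cannot pull them apart. Nor could a statistical analysis plan, because no analysis can supply a comparator that the design lacks.

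What is at stake is the study's central conclusion. If the wording stands, a significant before-after change in knowledge would be reported as evidence that the education was effective. A change in sprint, jump, grip or body composition would be read through the title as a result of the education. The protocol's own description supplies competing explanations for each.

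**Working it through.** **1. The plan's own figure.** Inputs from the Participant section: n = 30, d = 0.8, two-sided alpha 0.05, paired t-test. Power is P(|T| > t(0.975, 29)), where T is noncentral t with 29 df and noncentrality d√n = 0.8 × √30 = 4.38. The result is 0.988, where the protocol states 0.95. That mismatch is a separate matter and does not decide this point. What matters here is that power to detect a before-after difference is equally power to detect a drift of the same size.

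**2. What the mean change estimates.** For each outcome:

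expected mean change = education effect + background change over the four weeks.

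One observed mean cannot identify two unknowns.

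**3. Which background changes apply to which outcome.**

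| Outcome | Growth | Team training | Retesting |
|---|---|---|---|
| Players' performance | yes | yes | yes (same tests repeated) |
| Players' body composition | yes | yes | not a learning effect |
| Parents' knowledge score | no | no | yes (same questionnaire) |

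**4. Size under assumed drift.** Set the education effect to zero and let the group shift by δ SDs of the paired differences. Noncentrality is δ√30 = 5.477δ, with the same test as in step 1. The protocol gives no drift, so δ is assumed over a range.

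| Assumed drift δ | Noncentrality | Chance of a significant change |
|---|---|---|
| 0 | 0 | 5% |
| 0.1 | 0.55 | 8% |
| 0.2 | 1.10 | 19% |
| 0.3 | 1.64 | 36% |
| 0.4 | 2.19 | 56% |
| 0.5 | 2.74 | 75% |

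Because noncentrality grows with √n, more players would raise these chances for any fixed non-zero drift.

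**5. Would adjusting for training minutes and age help?** Regress the change D on mean-centred covariates by least squares. The intercept is mean(D) − Σ bⱼ × mean(centred xⱼ). Each centred mean is 0, so the intercept equals mean(D). The adjusted mean change is exactly the unadjusted one, and the average contribution of training and growth stays in it. If the covariates explain variance, the standard error shrinks and a pure drift is declared significant more often.

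**The case against.** The strongest reply is that the protocol is open about its design, calling it single-group and quasi-experimental, and that it includes sensible safeguards: a familiarization trial, standardized measurement conditions with one operator, and a verified training diary. Participation was May to July 2023, so the design cannot be changed. The drift table is the ordinary paired-t power curve at n = 30 with drift in place of effect, and nothing in the protocol places this study at 0.1 rather than 0.5. All of this is fair. It lowers the severity, but it does not make the change attributable. The safeguards may reduce noise or part of the practice effect; they are not a comparator.

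Several stronger readings are tempting, and the document does not support them:

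- *The protocol states an aim of proving effectiveness for performance and body composition.* It does not. There is no aims section in the text shown. The word effectiveness is attached only to the parents' knowledge test, and the link to the players' outcomes is read from the title.
- *All three rival explanations threaten the knowledge score.* Children's growth and training do not change a parent's test score. Of the three, only retesting applies.
- *The bias is known to favour the education.* The protocol gives no drift and does not say which direction of weight, BMI or waist change counts as benefit. The direction is not shown for body composition.
- *Any drift makes the test significant.* At 0.1 SD the chance is 8%.
- *Training volume is collected but never used.* Its use may be set out in a statistical analysis plan that was not available, so silence here is not a fault.

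**Conclusion.** The point holds as a limit on inference. The design can estimate within-group change over four weeks. It cannot establish that the education was effective for parents' knowledge, nor support the effect on performance and body composition that the title implies. That conclusion follows from the design alone and needs no numerical assumption.

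The 8% to 75% range does rest on assumptions: zero education effect, a common drift of 0.1 to 0.5 SD of the differences, 30 complete pairs and the paired t-test named in the protocol. It illustrates how readily drift could pass for an effect and does not estimate the drift in this study. The point should be fixed, but because the design is openly declared and the remedy is wording, it is not of the most serious grade.

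**What to change.** - In Procedures, replace the effectiveness wording with: *describe the change in parents' knowledge score from before to after the education*.
- State for all outcomes, including performance and body composition, that results are uncontrolled within-group changes over four weeks and cannot be attributed to the education. Name growth, team training and repeat testing as alternative explanations for the players' outcomes as they apply, and retaking the same questionnaire for the knowledge score. Read the title in that light.
- Do not offer a model with centred training minutes and age as a remedy for this problem. It returns the same mean change and removes none of the bias.

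The cost is a few sentences and a more modest claim. No new data or analysis is needed.

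### The stated post-hoc power of 0.95 does not follow from 30 pairs, alpha 0.05 and d = 0.8, and one large effect does not support the medium-to-large claim

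*Protocol*

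**What the plan says.** All of the power material is in the Participant section of the protocol. The number of players was not derived from a power target: "The sample size was determined based on feasibility within the basketball team context". A retrospective calculation follows: "A post-hoc power analysis was performed using G*Power 3.1 software for a two-tailed paired-sample t-test". Its inputs are given as "With an α level of 0.05, a sample of 30 participants, and an observed large effect size", with Cohen's d put at 0.8. The achieved power, it reports, "was 0.95. Therefore, the study was sufficiently powered to detect medium-to-large differences between pre- and post-education measurements". The next sentence then compares this power level with that of earlier studies in young athletes.

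The section does not say which outcome produced the 0.8, which SD standardises it, or what the pre-post correlation was. Later sections describe several kinds of outcome: a parental knowledge score, dietary intake, anthropometry and body composition, and performance, of which the protocol says "The testing session included a 20-m sprint, vertical jump, handgrip strength, and sit-and-reach flexibility test".

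**The concern.** There are two faults. First, test, sidedness, alpha, number of pairs, effect size and result are all stated, so the result should be reproducible. On the usual definition of the effect size for a paired test it is not.

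Second, the conclusion reaches further than the calculation. Power was evaluated at one effect, which the text itself calls large, and the inference drawn covers medium effects and pre-post measurements in general. Power at a large effect does not establish power at a medium one, and an effect from one unidentified outcome does not speak for the others.

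At stake is the protocol's only quantitative statement about whether 30 players are enough. A reader may rely on it when interpreting a non-significant change in one of the performance or body-composition measures.

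**Working it through.** **Inputs** (Protocol, Participant): two-sided paired t-test; alpha 0.05; n = 30 pairs; d = 0.8, described as observed; stated power 0.95.

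**Formula.** Write dz for the mean difference divided by the SD of the differences. Then df = n − 1, the noncentrality is λ = dz·√n, and power = P(T > t*) + P(T < −t*), where T is noncentral t and t* is the two-sided 5% critical value.

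**Step 1: the plan's own figure, d read as dz.** df = 29 and λ = 0.8 × √30 = 0.8 × 5.477 = 4.38. Power = **0.988**, against the stated 0.95, a gap of 3.8 percentage points. The normal approximation gives 0.992.

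**Step 2: could rounding of d explain it?** At n = 30, dz = 0.75 gives 0.978 and dz = 0.85 gives 0.994. No value that prints as 0.8 gives 0.95.

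**Step 3: could another test or setting explain it?** Each row keeps d = 0.8.

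| Variant | Power |
|---|---|
| One-sided paired | 0.996 |
| Two-sided paired, alpha 0.01 | 0.939 |
| Wilcoxon, relative efficiency 0.955 | 0.985 |
| Wilcoxon, relative efficiency 0.864 | 0.975 |
| Two independent groups of 30, two-sided | 0.861 |
| Two independent groups of 15, two-sided | 0.562 |

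None gives 0.95. The nearest, alpha 0.01, contradicts the stated 0.05.

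**Step 4: what would give 0.95?**
- With 30 pairs: dz = 0.68.
- With dz = 0.8: about 22 pairs (22 give 0.947, 23 give 0.956).
- With d on the raw SD and equal pre and post SDs: dz = d/√(2(1 − r)). Setting 0.681 = 0.8/√(2(1 − r)) gives 2(1 − r) = (0.8/0.681)² = 1.38, so r = 0.31. Power rounds to 0.95 for r of about 0.292 to 0.329.

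**Step 5: the medium end.** The protocol does not define medium, so the conventional 0.5 is assumed here.
- On the dz scale, n = 30: λ = 0.5 × 5.477 = 2.74 and power = **0.754**. Reaching 0.80 takes 34 pairs (33 give 0.795, 34 give 0.808).
- On the raw-SD reading that rescues 0.95, for the same outcome and correlation: dz = 0.5/√1.38 = 0.426 and power = 0.616 (0.605 to 0.628 over the band of r in step 4).
- Other outcomes may have other correlations. None is stated, so these are assumed:

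| Assumed r | Power at raw-SD d = 0.5, n = 30 |
|---|---|
| 0.31 | 0.62 |
| 0.50 | 0.75 |
| 0.554 | 0.80 |
| 0.60 | 0.84 |
| 0.70 | 0.93 |

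**Step 6: sensitivity of the fixed sample.** Solving for dz at n = 30 and two-sided 0.05 gives 0.529 for 80% power, 0.612 for 90% and 0.681 for 95%.

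**The case against.** The best defence is that the protocol says Cohen's d without naming the SD. On the raw-SD reading, a correlation of about 0.31 returns 0.95, and nothing in the document rules that correlation out. The fault would then be an unstated input and not wrong arithmetic. This stands as a possibility, but it leaves the figure irreproducible and does not rescue the conclusion, because power at d = 0.5 for that same outcome is then only about 0.62.

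A related point is that the misreported number might be d or the number of pairs and not the power. The document cannot settle this, so the software output should be checked before any figure is replaced. The sensitivity figures in step 6 hold for 30 pairs at any value of the observed effect.

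On the medium end, the shortfall is modest. On the dz scale 80% power begins at 0.53 against a benchmark of 0.5 that the protocol does not itself set, and it names no 80% threshold either. With a high enough correlation, a raw-SD effect of 0.5 is well powered. The criticism is therefore that the claim is unsupported as written, not that it is false for every outcome.

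Outcome designation may also sit in an analysis plan that is not at hand. The point here is narrower: an effect reported as observed was observed on something, and the sentence that relies on it does not say what.

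Finally, power computed from the observed effect largely restates the result and cannot show that the design was adequate. That is a further reason to prefer a sensitivity statement to a corrected observed power.

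**Conclusion.** The concern holds, and it is minor. With d on the SD of the differences, the stated inputs give power of 0.988, not 0.95, and no rounding of d or standard variant that keeps those inputs closes the gap. Only a raw-SD d with an unstated correlation near 0.31 does. The medium-to-large conclusion does not follow from one calculation at a large effect on an unnamed outcome. At 0.5, power is 0.75 on the dz scale, and on the raw-SD scale it depends on a correlation that is not given.

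The result rests on the exact noncentral t, 30 complete pairs, equal pre and post SDs for the raw-SD reading, and 0.5 as the conventional medium effect. The practical effect is small. Feasibility set the sample size, the stated 0.95 is conservative on the dz reading, and sample size, conduct and estimates are unaffected.

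**What to change.** Keep the feasibility rationale and amend the rest of the paragraph:

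1. Check d, n and power against the G*Power output and correct whichever was misreported.
2. State how d is standardised. If by the SD of the differences and d = 0.8 is confirmed, give the power as 0.99. If by the raw SD, say so and give the pre-post correlation used.
3. Name the outcome on which the effect was observed.
4. Replace the medium-to-large sentence with, for example: *Thirty pairs give 80%, 90% and 95% power for a standardised paired difference (mean difference over the SD of the differences) of 0.53, 0.61 and 0.68 at two-sided alpha 0.05; power at 0.5 is 0.75.*
5. Bring the following sentence, which compares the power level with earlier studies, into line with the corrected figure, after checking that those studies still support it.

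Deleting the post-hoc claim and keeping only the sensitivity statement is an acceptable alternative. The cost is wording only, with a slightly less favourable statement about medium effects.

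### Does the protocol's mixed account of who filled in the 3-day food record, parents or players, put the before-after comparison of diet at risk?

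*Protocol*

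**What the plan says.** The protocol describes the collection of dietary data in three places.

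- **Procedures** names one method: "A retrospective 3-day food consumption record form was utilized employing the retrospective recall method". It also fixes the mix of days (two weekdays and one weekend day, averaged). For the second assessment it says "The same questionnaire and forms were administered to the" parents.
- **Dietary Assessment, first sentence**, agrees with this: the parents "were requested to complete the 3-day food consumption record form in detail, utilizing the retrospective recall method" on behalf of the players.
- **Dietary Assessment, second sentence**, changes the subject: "Players were instructed to complete a 3-day food consumption record over three consecutive days". It allows two blocks, Thursday to Saturday or Sunday to Tuesday. The next sentence, whose subject is grammatically still the players, asks for foods, water, quantities and cooking method.

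Other consistency rules are explicit. All records were "entered into the Nutrition Information System by the same registered dietitian to ensure consistency", and one operator took the body measurements. The design is stated under Participant: "A single-group pre-post quasi-experimental design was used".

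**The concern.** Recall by a parent and a record kept by a child aged 8 to 13 are different measurements of intake. Two adjacent sentences appear to prescribe one each, and nothing says which supplied the analysed values or how they were combined. The protocol fixes the coder of the records and the operator for body measurements. It does not say that each child had the same individual reporter and the same block of days at both visits. The Nutrition Education Module section, which describes "their parents (e.g. mother, father and/or other primary caregivers", shows that a child could have more than one adult involved.

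There is no control group to absorb such a change. If many children moved in the same direction from one reporter or method to another, the difference between the methods would appear as a change in intake and could be read as an effect of the education.

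**Working it through.** **Figures in the protocol.** None bears on this point. The only design figure, the post-hoc power under Participant, does not involve how diet was recorded.

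**Step 1: the sentences side by side.**

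| Item | Procedures | Dietary Assessment, first sentence | Dietary Assessment, second sentence |
|---|---|---|---|
| Instrument | 3-day form | 3-day form | 3-day record |
| Reporter | parents named for the second visit | parents | players |
| Method | recall | recall | not stated; only the days are given |
| Days | 2 weekdays + 1 weekend day | not stated | Thu-Fri-Sat or Sun-Mon-Tue |
| Second visit | same forms, to the parents | not stated | not stated |

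The only firm clash is in the reporter row. The second sentence says which days were covered and what was written down. It does not say that entries were made as the food was eaten, and three named consecutive days can also be recalled afterwards. The section then speaks of the completed record in the singular, which fits one form per child better than two parallel methods.

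**Step 2: the day blocks.** Thu-Fri-Sat has Thursday and Friday as weekdays and Saturday as the weekend day (2 + 1). Sun-Mon-Tue has Sunday as the weekend day and Monday and Tuesday as weekdays (1 + 2). Both meet the rule in Procedures, so there is no contradiction. Holding each child to one block would be an added restriction, not a correction.

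**Step 3: the size of the bias if children did switch.** Inputs: n = 30 (Participant); k = net number of children switching in one direction (not in the protocol); D = mean difference between the two methods or reporters (not in the protocol).

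Shift in mean change = (k / 30) × D

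- k = 0: shift = 0.
- k = 1: shift = D/30 = 3.3% of D.
- k = 30: shift = D.

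Switches that balance in direction leave the mean unbiased but can widen the SD of change.

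To show what a shift could do, suppose the education has no effect and a uniform shift is measured in SDs of change. The two-sided 5% paired t-test with 30 pairs then rejects with these probabilities:

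| Assumed shift (SDs of change) | Rejection probability |
|---|---|
| 0 | 5% (nominal) |
| 0.1 | 8.3% |
| 0.2 | 18.5% |
| 0.3 | 35.5% |
| 0.5 | 75.4% |

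For example, if D were 0.5 SD, a shift of 0.1 SD would need k = 30 × 0.1 / 0.5 = 6 net switches. Both inputs are assumptions. The protocol documents no switch, and its repeated-forms sentence points to k = 0.

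**Step 4: what an added analysis would give.** One possible response is to repeat the paired comparison only in children with the same reporter, method and days at both visits. The 95% confidence half-width in SDs of change is t(0.975, n−1)/√n. The last column is the standardised change detectable with 80% power at two-sided 0.05. The sizes 20 and 15 are illustrative.

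| Pairs | Half-width | Detectable change |
|---|---|---|
| 30 | 0.373 | 0.53 |
| 20 | 0.468 | 0.66 |
| 15 | 0.554 | 0.78 |

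The subset loses precision, and it can be formed only if the forms happen to record these items. If nobody switched, it is the main analysis again. A second possible response is the ratio of reported energy intake to basal metabolic rate, which is available because "Basal metabolic rate was estimated via the BIA device output". That ratio cannot tell a true change in intake from a change in reporting.

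**The case for a change.** The strongest argument for acting is that the text is inconsistent on its face, that reporter and method are matters of data collection and not of the SAP, and that consistent coding by one dietitian cannot repair an inconsistent source. Naming the reporter would cost almost nothing. The repeated-forms sentence also leaves the instruction to players unexplained and does not identify which parent answered.

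Part of this stands. The protocol does not say who completed the form, and a careful reader will want to know. The step from there to a threatened comparison is not supported. The repeated-forms sentence covers the instrument and the parent as the class of reporter. The list of mother, father and other caregivers describes who attended the education session, not who filled in forms, so it is no evidence that respondents changed. The weight of 1/30 per child holds for any conjectured error in a mean of 30 and does not show that an error occurred.

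A separate worry is that reports of diet may drift towards the taught answers after the education. That would be present with one reporter and one method throughout, so settling who filled in the form would not remove it.

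**Conclusion.** No change to the plan follows. The Dietary Assessment section is loosely worded on one item, who completed the 3-day form. The natural reading, supported by Procedures and by the sentence just before the one about players, is that parents reported by recall on the same form at both visits, perhaps with the players' help. On that reading the bias is zero.

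This conclusion rests on two assumptions: that the repeated-forms sentence describes what was done, and that the sentence about players describes the days and content of the same form and not a second, prospective method. If either were false, the bias would be (k/30) × D. The protocol gives neither quantity, so no size can be claimed.

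The data come from May to July 2023 and the document is dated December 2025, so rewording cannot alter how intake was collected. The authors can name the actual reporter when they describe their methods. That is a reporting clarification and leaves the paired comparison of intake as it is.
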